# 11.6 Procedures for Collecting and Recording Adverse Events

Abnormal clinical findings from medical history, examination or blood tests will be assessed by a blinded delegated clinician / Investigator as to their clinical significance.

RECRef: 23/SC/0268 NIV001: A study of a new vaccine against Nipah Page 44 of 71

All AEs that are observed by the Investigator or reported by the participant irrespective of their relatedness to the study vaccination will be recorded from the day of vaccination for 28 days. These will be recorded in either the eDiary (by the participant) and/or eCRF (by blinded study investigators). Outside of this window (i.e. from 28 days after each vaccination and until the point of a subsequent vaccination or until the final visit if vaccination course completed), non-serious AEs will only be recorded if they require medical attention (contact with GP, visit to emergency department). These will be recorded in the eCRF.

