### **6 OBJECTIVES AND ENDPOINTS**

# 6.1 Objectives, Outcome Measures and Evaluation Timepoints

Outcome	Objective	Outcome measure	Evaluation timepoints 
Primary	To assess the safety and tolerability of ChAdOx1 NipahB in healthy volunteers aged 18-55	a) Occurrence of solicited local reactogenicity signs and symptoms b) Occurrence of solicited systemic reactogenicity signs and symptoms c) Occurrence of unsolicited adverse events (AEs) d) Occurrence of abnormal safety laboratory measures	7 days following each vaccination
		e) Occurrence of serious adverse events (SAEs) and adverse events of special interest (AESIs)	Cohort 2 : D0, D1, D14, D28, V2, V2+1, V2+14, V2+28 Duration of the study (D0 to V2+281)
Secondary	To assess the immunogenicity of ChAdOx1 NipahB vaccine in healthy adult volunteers aged 18-55	NipahB glycoprotein G-specific serological response as measured by ELISA	Cohort 1: D0, D14, D28, D56, V2, V2+14, V2+28, V2+56, V2+281 Cohort 2: D0, D14, D28, V2, V2+14, V2+28, V2+281
Exploratory 	Immunological profiling	a) NipahB neutralising antibody responses measured by live or pseudoneutralisation assays b) NipahB glycoprotein G T cell response measured by IFN-g ELISPOT c) Cellular immune response to Nipah virus measured by ICS, proliferation and/or whole blood assays	Timepoints will be detailed in the laboratory analysis plan
	To assess anti-PF4 antibody levels following vaccination	Change in anti-PF4 antibody level measured by ELISA	D0, D14, V2+14
	To assess anti-vector immunity following vaccination	Binding and/or neutralising antibody responses against ChAdOx1	Timepoints will be detailed in the laboratory analysis plan

Visit and procedure timepoint windows are defined in section 4 (Schedule of Procedures). These exploratory endpoints may be performed; additionally, sample analysis for the completion of exploratory endpoints may be performed under the ethically-approved Oxford Vaccine Centre (OVC) Biobank protocol (REC 21/SC/0161). Further exploratory assays/analyses may be carried out (see section 9.6.2).

RECRef: 23/SC/0268 NIV001: A study of a new vaccine against Nipah Page 26 of 71

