#### 11.12 Laboratory AEs

Severity grading for laboratory AEs are defined in Appendix B: Severity Grading Scales. All changes in laboratory values will be recorded as AEs if they are of Grade 2 severity or above. Changes of laboratory values of Grade 1 severity may be recorded as AEs if they are judged to be clinically significant by a blinded PI-delegated clinician / Investigator.

If a test result is deemed clinically significant, it may be repeated to ensure it is not a single occurrence or spurious result. If a test result remains clinically significant, the participant will be informed and advised with regards to appropriate medical care. If abnormal laboratory values are the result of pathology for which there is an overall diagnosis, then this diagnosis will be reported as one AE only.

A Grade 4 laboratory AE will be considered a SAE.

RECRef: 23/SC/0268 NIV001: A study of a new vaccine against Nipah Page 46 of 71 IRAS project ID: 1007433 Virus in adults aged 18 to 55

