#### 13 STATISTICS

#### 13.1 Study Analyses

# 13.1.1 Descriptive Statistical Methods

The analyses for this study will be descriptive in purpose and will not include any hypothesis testing, power calculations, or presentation of p-values for group comparisons.

Counts and percentages of local and systemic solicited adverse reactions from eDiaries during days 0-6 following each vaccination will be presented for each group. Unsolicited AEs occurring during days 0-27 following each vaccination, and all SAEs and AESIs occurring throughout the duration of the study will be summarised.

Highly skewed antibody and cellular response data will be log-transformed prior to analysis. The geometric mean titres (GMTs) and associated 95% confidence intervals (CIs) will be summarised by computing the anti-log of the mean of the log-transformed data. Medians and interquartile ranges of the untransformed data may additionally be presented.

Due to the descriptive nature of the trial, no testing will be performed between groups.

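### Sections 11.6 and 11.12 give opposite instructions for recording Grade 2-3 laboratory abnormalities found from day 28 after a dose without medical attention

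*Protocol*

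**What the plan says.** Protocol section 11.6 opens by bringing abnormal findings from history, examination and blood tests under clinical assessment. It then states that all AEs, related or not, "will be recorded from the day of vaccination for 28 days". For the remaining time, "from 28 days after each vaccination and until the point of a subsequent vaccination or until the final visit if vaccination course completed", the rule changes: "non-serious AEs will only be recorded if they require medical attention (contact with GP, visit to emergency department"). It makes no exception for laboratory findings.

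Section 11.12 covers laboratory AEs and sets no time limit: "All changes in laboratory values will be recorded as AEs if they are of Grade 2 severity or above". Grade 1 changes may be recorded if judged clinically significant. At the top of the scale, "A Grade 4 laboratory AE will be considered a SAE".

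In section 6.1 the fourth primary outcome is "d) Occurrence of abnormal safety laboratory measures". For Cohort 2 the evaluation visits are "D0, D1, D14, D28, V2, V2+1, V2+14, V2+28", which match the safety bloods in Table 3. Section 13.1.1 describes the AE summaries: "Unsolicited AEs occurring during days 0-27 following each vaccination, and all SAEs and AESIs occurring throughout the duration of the study will be summarised".

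**The concern.** Both rules apply to the same blood result and give different answers. The first 28 days are days 0 to 27 (sections 11.8 and 11.9.2 count them this way), so a bleed on the nominal D28 visit falls on the first day of the restricted period. Suppose the ALT or neutrophil count on that day is Grade 2 or 3 and the participant has had no contact with a GP or emergency department. Section 11.12 makes this an AE. Section 11.6 says not to record it.

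Most such findings would be asymptomatic, so the medical-attention condition would rarely be met. Several processes depend on an AE existing: the causality assessment in 11.3, the follow-up of related AEs in 11.14, and the AE summaries available to the DSMC under 11.22.1. DSMC reviews 2, 3 and 5 include data up to 28 days after a dose, which is the visit where the rules diverge. This is a first-in-human trial with safety as its primary objective. A recording rule that depends on which day the participant attends makes the AE listing uneven between participants for no clinical reason.

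**Working it through.** The plan gives no figure on this point, so the check is a count of scheduled safety bloods against the 11.6 window.

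**Inputs**
- Cohort 1, n = 6 (Table 2): safety bloods at D0, D2, D7, D14, D28, D56, V2, V2+2, V2+7, V2+14, V2+28 and V2+56. That is 12 visits, 11 of them after baseline.
- Cohort 2, n = 45 (Table 3): safety bloods at D0, D1, D14, D28, V2, V2+1, V2+14 and V2+28. That is 8 visits, 7 of them after baseline.
- Unrestricted recording window (11.6): days 0-27 after each dose.
- Visit windows (Tables 2 and 3): D28 and V2+28 ±3 days; V2 ±14 days around D84; D56 and V2+56 ±7 days.

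**Denominator**

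Planned post-baseline draws = 6 × 11 + 45 × 7 = 66 + 315 = 381.

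**Draws nominally in the restricted period**
- Cohort 1: D28, D56, V2, V2+28, V2+56 = 5 per person, 6 × 5 = 30.
- Cohort 2: D28, V2, V2+28 = 3 per person, 45 × 3 = 135.
- Total 30 + 135 = 165, and 165/381 = 43%.

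V2 is counted here because the restricted period runs until the next vaccination and section 9.4.1 lists the blood draw before the injection.

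**Sensitivity to how the windows are read**

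| Reading | Draws in the restricted period | Share of 381 |
|---|---|---|
| Nominal days, V2 outside the window | 6 × 5 + 45 × 3 = 165 | 43% |
| Nominal days, V2 inside as a vaccination day | 6 × 4 + 45 × 2 = 114 | 30% |
| All D28 and V2+28 bleeds on days 25-27, V2 outside | 6 × 3 + 45 × 1 = 63 | 17% |
| All D28 and V2+28 bleeds on days 25-27, V2 inside | 6 × 2 = 12 | 3% |

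The last row leaves only D56 and V2+56, which apply to 6 of 51 participants. Including the 51 baseline draws makes the denominator 381 + 51 = 432, and the nominal share 165/432 = 38%.

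**Dependence on visit day**

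The ±3-day window allows a D28 bleed on any of days 25 to 31. Days 25, 26 and 27 fall under full recording. Days 28, 29, 30 and 31 fall under the medical-attention condition. The same Grade 2 value would be recorded on day 27 and, under 11.6, not on day 28.

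**What the conflict does not reach**
- Grade 4 laboratory values are SAEs (11.12), collected throughout (11.15).
- Thrombocytopenia is an adverse event of special interest (AESI; 11.2, Table 5), recorded throughout.
- Any abnormality that led to medical contact is recorded under both sections.

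**The case against.** The strongest reply is that 11.12 is the specific rule for laboratory AEs and prevails over the general rule in 11.6, whose examples (GP contact, emergency visits) suit events reported by participants. That is a reasonable reading, and site staff may well follow it. But the protocol does not say so. Section 11.6 names blood tests in its first sentence and allows no laboratory exception, so staff who follow it literally would be following the protocol.

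A reader might go further and infer that these values are lost from primary outcome (d). The documents do not support that. Outcome (d) is defined on abnormal laboratory measures at listed visits, separately from unsolicited AEs. Section 12 holds clinical laboratory data in the database, section 13.1.5 uses all available data, and Appendix B allows every stored value to be graded. Outcome (d) would be under-counted only if it were derived from recorded AEs, which the protocol does not state.

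A reader might also take section 13.1.1 to mean that late laboratory abnormalities appear in no summary. Its days 0-27 limit is stated for unsolicited AEs, and the tabulation of (d) may properly sit in the statistical analysis plan, which was not available.

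Nor do the documents show that the holding rules fail. The group rule in 11.24.1 refers to events that participants experience, not to events recorded under 11.6. The individual laboratory rule covers only 7 days after vaccination. Section 11.19 has investigators review safety bloods directly.

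Finally, 43% is an upper bound on draws where the rules could conflict, not a rate of lost events. That stands.

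**Conclusion.** The contradiction is real and should be reconciled. For non-serious Grade 2-3 laboratory abnormalities found from day 28 after a dose without medical attention, 11.12 requires an AE record and 11.6 does not allow one. It touches up to 165 of 381 planned post-baseline safety draws (43%), or 114 (30%) if V2 is treated as inside the window. It could be as low as 12 (3%) if, in addition, every D28 and V2+28 bleed fell on days 25-27.

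These counts assume full enrolment of 6 and 45 and complete attendance. The number of abnormalities affected cannot be stated, because the protocol gives no rate for Grade 2-3 laboratory changes.

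The consequence is limited to the AE record and what follows from it: causality assessment, follow-up of related AEs and AE summaries for the DSMC. The laboratory values remain available. Stored values can be re-graded at analysis, but a blinded causality assessment made at the time, and follow-up, cannot be recreated.

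**What to change.** Reconcile the two sections with one sentence in 11.6: the medical-attention condition does not apply to laboratory AEs from scheduled safety bloods, which are recorded as in 11.12 at every such visit. This also settles the status of the pre-dose V2 draw and removes the dependence on visit day within the ±3-day window.

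In addition, confirm in section 13.1.1 or in the statistical analysis plan that outcome (d) is summarised from the laboratory values at all timepoints in section 6.1, not from the AE log.

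The change needs a short amendment and no new sampling, because the bloods are already scheduled and the results already held. The cost is a few more AE forms and possibly slightly higher laboratory AE counts.

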#### 11.7 Solicited Adverse Events

Predefined local and systemic solicited AEs for reactogenicity assessment, as listed in Table 7, will be collected in an electronic diary for 7 days (on days 0-6) following administration of the vaccine. Participants will measure and record their temperature and the diameter of any injection site redness with a provided thermometer and tape measure respectively, and AE severity gradings will be classified based on these measurements. For all other solicited AEs, solicited AE severity will be self-assessed by participants according to severity grading scales provided to them as defined in Appendix B: Severity Grading Scales.

Table 7 Solicited Adverse Events

Local solicited AEs	Systemic solicited AEs
Redness at the injection site (measured)	Fever (measured)
Warmth at the injection site	Chills
Itch at the injection site	Feverishness
Pain at the injection site	Joint pains
Swelling at the injection site	Muscle pains
	Fatigue
	Headache
	Nausea
	Malaise

# 11.8 Unsolicited Adverse Events

Unsolicited adverse events i.e. those collected through open questioning e.g. "did you experience any new symptoms?" (which are not solicited adverse events on days 0-6 following vaccination and do not constitute SAEs or AESIs) will be collected for 28 days (on days 0-27) following administration of the IMP. These will be recorded in the participant's eDiary and then recorded by the study team in the relevant eCRF.

RECRef: 23/SC/0268 NIV001: A study of a new vaccine against Nipah Page 45 of 71 IRAS project ID: 1007433 Virus in adults aged 18 to 55

#### 11.9 eDiary AEs

#### 11.9.1 eDiary Collection of Solicited Adverse Events

From the time of each vaccine administration up to 7 days post-vaccination (day of vaccination and six subsequent days), solicited adverse events will be recorded by the participant in an electronic diary and graded by the participant. If further action is required following an AE including face-to-face medical review and/or prescribed medication, this will be recorded by the study team in the eCRF. Causality will be assigned by blinded PI-delegated clinician / Investigator. Any solicited AE which meets the definition of a SAE will be managed and reported as per Section 11.15.

#### 11.9.2 eDiary Collection of Unsolicited Adverse Events

From the time of each vaccine administration up to 28 days post-vaccination (day of vaccination and 27 subsequent days), unsolicited adverse events will be collected using the eDiary and reviewed at clinic visits. If a participant records a grade 3 or 4 adverse event, an email alert is sent to the investigator(s), so that the investigator is aware and can review appropriately. If clarification of any event is required then the study nurse or doctor will seek this from the participant during a clinic visit or by telephone call. These unsolicited adverse events will be recorded in the AE section of the eCRF. Unsolicited adverse events recorded in the eDiary will be severity-graded by the participant. Causality will be assigned by the blinded PI-delegated clinician / Investigator as per section 11.3.

#### 11.10 Observation Related AEs

Physical observations of the patient (e.g. temperature, blood pressure, heart rate) will be taken according to the schedule of procedures. These will be recorded in the eCRF. If abnormal, a severity grading will be assigned by the study team as per Appendix B: Severity Grading Scales.

#### 11.11 Visit Elicited AEs

Participants will be asked about the occurrence of AEs, and if any are elicited they will be recorded in the eCRF and graded by a blinded PI-delegated clinician / Investigator.

#### 11.12 Laboratory AEs

Severity grading for laboratory AEs are defined in Appendix B: Severity Grading Scales. All changes in laboratory values will be recorded as AEs if they are of Grade 2 severity or above. Changes of laboratory values of Grade 1 severity may be recorded as AEs if they are judged to be clinically significant by a blinded PI-delegated clinician / Investigator.

If a test result is deemed clinically significant, it may be repeated to ensure it is not a single occurrence or spurious result. If a test result remains clinically significant, the participant will be informed and advised with regards to appropriate medical care. If abnormal laboratory values are the result of pathology for which there is an overall diagnosis, then this diagnosis will be reported as one AE only.

A Grade 4 laboratory AE will be considered a SAE.

RECRef: 23/SC/0268 NIV001: A study of a new vaccine against Nipah Page 46 of 71 IRAS project ID: 1007433 Virus in adults aged 18 to 55

#### 11.13 Notes on Recording AEs

Pre-existing medical conditions (present prior to enrolment into the study) are considered "concurrent medical conditions" and should not be recorded as AEs. However, if the participant experiences a worsening or complication of the condition, the worsening or complication should be recorded as an AE. Study staff will ensure that the AE term recorded captures the change in the condition (e.g., "worsening of").

Each AE will be recorded to represent a single diagnosis. Accompanying signs or symptoms (including abnormal laboratory values) will not be recorded as additional AEs.

Any pregnancy occurring during the clinical study and the outcome of the pregnancy should be recorded and followed up for congenital abnormality or birth defect at which point it would fall within the definition of "serious" and the congenital abnormality of birth defect would be reported as an SAE. Pregnancy notification and follow-up reports on pregnancy outcome will be provided to the DSMC with the ongoing consent of the participant.

# 11.14 Following Up of AEs

AEs considered related to the vaccine or placebo will be followed until resolution, the event is considered stable or until non-study causality is assigned. At the end of the study all other ongoing/open AEs will be assessed by a blinded PI-delegated clinician / Investigator, to ensure, if not already done so, adequate medical follow-up (if required) has been arranged, e.g. referral to the participant's GP.

All AEs that result in a participant's withdrawal from the study will be, subject to participant consent, followed up where possible until a satisfactory resolution occurs, or until a non-study related causality is assigned. This will involve an end of study assessment at which the requirement for further appropriate care under medical supervision will be determined. If required the participant will be referred to their GP for ongoing medical supervision, until symptoms cease or the condition is deemed resolved or stable.

# 11.15 Reporting Procedures for SAEs

SAEs will be collected throughout the entire trial period (from first vaccination to the final study visit or withdrawal).

All SAEs will be reported on the SAE form (paper or electronic) to the CI (as delegated by the Sponsor) immediately (or within 24 hours at the latest) of the site study team becoming aware of the event being defined as serious. Causality of SAEs will be assessed by the blinded investigator.

The CI on behalf of the Sponsor will be responsible for unblinding in the event of serious adverse reactions and will be responsible for the reporting of any SUSARs (as detailed in section 11.17). Any SUSAR must be reported to the DSMC.

Unrelated SAEs will be reported to the DSMC for discussion at the next scheduled DSMC review (11.22.1).

RECRef: 23/SC/0268 NIV001: A study of a new vaccine against Nipah Page 47 of 71

Additional information received for a case (follow-up or corrections to the original case) needs to be detailed on a new SAE form notified by the study team to the CI, who will then notify the DSMC.

The DSMC will perform an independent review of SAEs and request any further information required in a manner adherent to the procedures and timelines of the DSMC Charter. Documentation of this review will be kept in the TMF.

# 11.16 Events Exempt from Reporting as SAEs

Hospitalisation (including inpatient or outpatient hospitalisation) for an elective procedure for a preexisting condition that has not worsened unexpectedly does not constitute an SAE. Emergency department attendances should not routinely be reported as SAEs unless they meet the SAE definition described in section 11.1.

#### 11.17 SUSAR Reporting

All SUSARs will be reported to the Sponsor, relevant Research Ethics Committee and to the MHRA. Fatal or life-threatening SUSARs must be reported within 7 days and all other SUSARs within 15 days. Any additional relevant information should be sent within 8 days of the report.

The CI or delegate will also inform all Investigators concerned of relevant information about SUSARs that could adversely affect the safety of participants.

#### 11.18 Development Safety Update Report

The CI (on behalf of the Sponsor) will submit (in addition to the expedited reporting above) Development Safety Update Reports (DSURs) once a year throughout the clinical trial, or on request to the Competent Authority (MHRA in the UK), Ethics Committee, HRA (where required), Host NHS Trust (where required) and Sponsor.

The Development International Birth Date (DIBD) for ChAdOx1 NipahB is 19th October 2023 and the data lock point of each DSUR will be the last day of each one-year reporting period (18th October).

#### 11.19 Safety Profile Review

The safety profile will undergo blind review on a regular basis by the Investigators using the electronic diary, adverse events eCRF and safety bloods. Any concerns will be referred to the blinded CI. If the CI remains concerned they may consider unblinding and/or escalation to the unblinded DSMC as required.

#### 11.20 Trial Management Group

The CI and study site investigators will form the trial management group (TMG) and will provide ongoing management of the trial.

# 11.21 Data Safety Monitoring Committee (DSMC)

An independent DSMC will be appointed. There will be a minimum of three appropriately qualified committee members of whom one will be the designated Chair. The DSMC will operate in accordance with the NIV001 DSMC charter, which will be established before recruitment starts. The Chair of the

RECRef: 23/SC/0268 NIV001: A study of a new vaccine against Nipah Page 48 of 71

DSMC may also be contacted for advice where the Chief Investigator feels independent advice or review is required.

## 11.22 Interim Safety Reviews

# 11.22.1 Sequence of Enrolment and Vaccination

An initial cohort of 6 participants (Cohort 1) will be enrolled and receive their first vaccine prior to the enrolment of further participants. Enrolment will be staggered within Cohort 1 (Table 8). The first participant enrolled into the trial will be vaccinated alone, ahead of any other participants. Their profile of adverse events including day 2 laboratory results will be reviewed for at least 48 hours post-vaccination. Provided there are no safety concerns, as assessed by the PI, a further 2 participants will be vaccinated at least 1 hour apart from each other. The profile of adverse events for the second and third participants, including day 2 laboratory results, will then be reviewed by the PI after a further 48 hours and if deemed acceptable, the remaining 3 participants in the group may then be vaccinated.

Enrolment of the remaining participants in the trial (Cohort 2) will continue only after a positive decision from the DSMC following the first DSMC safety review (detailed in section 11.22.1).

**Table 8** Sequence of Enrolment (First Doses)

Sequence	Participant groups	Minimum interval before progressing to next step	Safety review before progression
Step 1	Cohort 1 volunteer 1	48 hours	Local safety review (PI)
Step 2	Cohort 1 volunteer 2	1 hour	Clinical team involved with vaccination
Step 3	Cohort 1 volunteer 3	48 hours	Local safety review (PI)
Step 4	Cohort 1 remaining volunteers	7 days	DSMC review
Step 5	Cohort 2	n/a	n/a

Administration of the second doses of vaccine to participants in Cohort 2 will only occur once participants in Cohort 1 have had their second vaccine doses and after an interim safety review conducted DSMC (detailed in section 11.22.1).

